APPENDIX 4 – List of prohibited strong CYP3A4 inducers and inhibitors	

1. SYNOPSIS

Title	g Mammary Stem Cells and Breast Cancer Prevention		
Design	Design Non-randomized, open-label, phase II, window of opportunity trial.		
	The overall purpose of this study is to determine if rapamycin can reduce malignant markers and MaSC number in surgical specimens.		
Objectives	 The primary objectives are: Reduction of MaSC in DCIS, LCIS, ALH or ADH in patients receiving rapamycin Reduction of malignant markers in DCIS, LCIS, ALH or ADH in patients 		
	receiving rapamycin The secondary objectives are: 1. Toxicity 2. Surgical complications		
Patient Population	Women (pre and post-menopausal) with DCIS, LCIS, ALH or ADH undergoing surgical resection.		
Treatment Plan	Women who consent will be given rapamycin for 5-7 days treatment at 2 mg/day. Patients will undergo mastectomy or lumpectomy 3-7 days after the last dose of rapamycin. Pathological and molecular biomarkers associated with breast cancer aggressiveness and recurrence will be assessed by the Breast Pathologist and the features of MaSCs will be determined by the PI's lab for determining the effect of rapamycin.		
Efficacy Assessment	Efficacy will be measured by measurement of MaSC and malignant markers in tissue from patients with DCIS, LCIS, ALH or ADH		

2. BACKGROUND AND SIGNIFICANCE

Aging – the No. 1 risk factor for breast cancer. Cancer incidence rises exponentially during midlife in humans and in mice¹. About 80% of all breast cancers arise in women over age 50 and age specific increase of invasive breast cancer results in a cumulative lifetime risk of 13.2% or 1 in 8 (http://www.srab.cancer.gov/devcan). Even for women carrying BRCA1 and BRCA2 mutations with family history of familial breast cancer, aging is another important risk factor². However, the knowledge regarding the cellular and molecular basis that links aging with clinical manifestation of breast cancer is indeed scanty³⁻⁵. Thus, understanding age-related changes, which promote breast cancer, should have a major impact on our ability to prevent and treat breast cancer for the high risk and the general aging population.

Does breast cancer originate from mammary stem cells? During aging, stem cells responsible for lifelong tissue maintenance and repair are susceptible to changes in their niche and genomic integrity. Recent evidences indicated that they may be responsible for neoplastic transformation. However, there is little direct experimental evidence linking aging mammary stem/progenitor cells to spontaneous preneoplastic transformation and tumorigenesis. Mammary stem cells (MaSCs) have been shown to have the potential to drive mammary gland development and to initiate neoplastic transformation when genetically altered⁶⁻³. Gene expression profiles of different subtypes of breast cancer have also been shown to correspond to the profiles of the basal or luminal mammary stem/progenitor cell-enriched epithelial cells, which suggests that MaSCs might be the origin of certain types of breast cancer. A recent study reported a shift in the balance between luminal and basal lineages in aging human breast cells and expansion of multipotent progenitor population with a basal differentiation bias⁹. These changes were postulated to contribute to aging-associated mammary tumorigenesis. As shown in our preliminary data below, we have demonstrated that aging is associated with increased number of aberrant MaSCs, which can generate mammary glands with early neoplastic lesions. Our study is the first experimental demonstration that MaSCs are the precursors of **spontaneous** neoplastic lesions and aging MaSCs appear to be predisposed to neoplastic transformation.

Role of aging/senescence-associated inflammatory response in tumorigenesis. Recent studies have suggested that senescent cells in the aged stroma might create a tissue microenvironment favoring cancer initiation and growth. Cellular senescence acts as a barrier to transformation, but it drives aging phenotypes and is also believed to induce a fertile ground for cancer development late in life¹⁰. Senescent cells increase with age in many mammalian tissues including human, primates and rodents^{11,12} and are found at sites of many age-related pathologies including benign prostatic hyperplasia^{13,14}. Senescent human and mouse cells secrete pro-inflammatory cytokines, chemokines, extracellular matrix components, and growth factors. A phenotype termed as senescence associated secretory phenotype (**SASP**) disrupts local tissue homeostasis and is believed to promote tumorigenesis.

Inoculation with premalignant or malignant epithelial cells together with senescent fibroblasts led to more and larger tumors in host mice than inoculation with the epithelial cells alone or with presenescent fibroblasts¹⁵. Using a *Cdkn2a*INK4A (p16)–luciferase reporter mouse model, one recent study found an exponential increase with age in senescence associated-expression of p16 and the induction of p16 in the benign stromal cells of the nascent neoplasm¹⁶. In our whole genome transcriptome analysis shown below, we found an inflammatory response both in the mammary stromal and MaSC-enriched cell compartments in association with senescent stromal cells. Although this senescence-associated inflammation response (**SIR**) has been shown in various tissues, it was only last year that SIR was shown to contribute to colon tumorigenesis in genetically modified mouse models¹⁷. However, it is not known whether the SIR causes the transforming phenotype of MaSCs during progressive aging.

3. PRELIMINARY DATA

Development of a novel in vitro assay for quantifying MaSCs. In order to quantitatively measure the effect of aging on the number and function of murine mammary stem/progenitor cells, we recently developed a novel in vitro method¹⁸. Previously, murine MaSCs were quantified with limited dilution in vivo transplantation of MaSC-containing mammary epithelial cells into de-epithelized inguinal mammary glands (also denoted as cleared mammary fat pads) of 21-day-old mice and subsequent examination of regeneration frequency of a fully functional mammary gland. This in vivo regeneration method requires large number of recipient mice for transplantation and a relatively long period (8 weeks) of experiment turnover, not to mention the associated expensive cost. Our in vitro method, termed sphere formation and differentiation (SFD) assay, involves suspension culture of mouse MaSC-enriched basal cells, which are FACS-sorted out with their cell surface immunophenotype of Lin-CD49fhighCD24med (Fig. 1A)^{19,20}, for the formation of mammospheres (Fig. 1B). These spheres were verified to be of clonal origin of single MaSC¹⁸, and they can be differentiated to form morphologically distinct solid 3D spherical structures/organoids when embedded in 3D extracellular matrix of Matrigel (3D-ECM) (Fig. 1C). Upon in vivo transplantation, these single mammospheres or 3D solid structures can generate full ductal-lobular outgrowths (Fig. 1D). We were able to visualize ductal structures of the regenerated mammary ducts with green fluorescence imaging (Fig. 1D) as the mammospheres and 3D solid structures were formed by MaSCs isolated from GFP-transgenic mice. Thus, this SFD assay allows quantification of MaSC in vitro.

[figure not shown]

Fig. 1. *in vitro* and *in vivo* assays for mouse MaSC qualification and quantification. Primary cells were sorted with FACS (A), and used for the following assays. Mammosphere assay (B): cells were cultured in a 96-well low attachment plate for 7 days in a mammosphere medium. 3D-ECM sphere differentiation assay (C): mammospheres were plated in Matrigel and cultured for 9 days to score 3D solid structures/organoids. *in vivo* transplantation assay (D): single mammospheres or 3D solid structures were injected into cleared mammary fat pad of a 21-day-old recipient female mouse. After 8 weeks, regenerated mammary glands were visualized with green fluorescence imaging.

Age-associated changes in MaSC frequency and gene expression. Using this SFD assay, we measured MaSC number as a function of aging. FACS analysis revealed that total basal epithelial cell frequency, which is percent of basal epithelial cells in total lineage negative (Lin-) mammary epithelial cells (MEC) (Fig. 1A), increased with progressive aging in C57BI/6 mice (Fig. 2). This aging-associated increase of basal epithelial cells and decrease of luminal epithelial cells (data not shown) led to a significant decrease in the luminal to basal epithelial cell ratio (Fig. 3A) and a significant increase in MaSC frequency (Fig. 3B) in old (22-30 month-old) mice of both C57BI/6 and Balb/c strains when compared to their respective young (4-6 month-old) cohorts. However, the ability of the 3D structures to regenerated 3D structures during serial passage in 3D culture was much lower by the old MaSC-formed 3D structures than by the young MaSC-formed 3D structures (data not shown). To elucidate molecular changes associated with aging MaSCs, we

used RNA-seq to profile whole transcriptome of FACS-sorted basal, luminal, stromal cells, and early stage mammospheres formed by basal or luminal epithelial cells, which are highly enriched in MaSCs or luminal progenitors respectively, from young and old C57BI/6 mice.

Using pairwise comparison among young mammary cells, we obtained a set of basal or luminal cell specific genes/markers, named Basal Signature or Luminal Signature respectively and performed gene signature enrichment analysis (**GSEA**) using the basal or luminal markers we identified as well as those previously reported by Lim et al.²¹. As shown in **Fig. 4**, the old basal (CD49fhighCD24med) cells and their mammospheres showed significantly reduced expression of basal markers, but significantly increased luminal markers. In contrast, GSEA did not show a significant change of the basal or luminal signatures in old luminal (CD49flowCD24high) cells and their mammospheres (data not shown). These findings indicate aberrant changes of old MaSCs towards a more luminal phenotype, which may contribute to their reduced self-renewal capacity and transforming property as described below.

[figure not shown]
[figure not shown]
[figure not shown]

Fig. 2. Representative FACS profiles of Lin MEC (luminal+basal fraction) from C57Bl/6 mice at different ages showing basal MaSC-enriched fraction (purple).

[figure not shown]

Fig. 4. Gene signature enrichment analysis show that old CD49f^{mgn} basal cells and their mammospheres (MMS) have reduced expression of basal markers derived from our RNA-seq or Lim et al, *Breast Cancer Res* **12**:R21, 2010, but have enriched luminal markers in comparison with young basal cells and their MMS respectively.

Old MaSC-mediated development of spontaneous neoplastic lesions. Significantly, *in vivo* transplantation of single 3D solid structures and subsequent histology analysis by a breast pathologist revealed that the ducts of the old MaSC-regenerated mammary glands were similar to the ducts of the old primary mammary glands with significantly higher number of hyperplastic and dysplastic foci of atypical ductal hyperplasia (ADH, indicated by abnormal glandular proliferation) and ductal carcinoma in situ (DCIS, indicated by numerous mitotic figures, nuclear enlargement, and coarse chromatin pattern) than those from the young primary glands and young MaSC-regenerated glands (Fig. 5A-C). We define the ability of generating the early neoplastic lesions in the MaSC-regenerated glands as the transforming phenotype/property of MaSCs. Interestingly, the cells in the dysplastic lesions of the old MaSC-regenerated glands express various luminal epithelial markers such as estrogen receptor alpha (ERα) and Her2 (Fig. 6) indicating their resemblance to human breast adenocarcinoma.

[figure not shown]

Fig. 5. Early neoplastic lesions in the primary and MaSC-regenerated glands. Primary and MaSC-regenerated mammary glands were processed for sectioning and H&E staining from each mouse. Normal, hyperplasic, and dysplastic (ADH: atypical ductal hyperplasia; DCIS: ductal carcinoma *in situ*) ducts (Panel A) in H&E stained slides were counted and presented as percent of total ducts in a given tissue section slide. Percent of hyperplastic and dysplastic ducts in sections of primary glands of young (solid dot) and old (circle) mice and their MaSC-regenerated glands is shown in Panels B and C. Each dot represents data from one mouse. P values were obtained with Student *t* tests.

[figure not shown]

Fig. 6. Old MaSC-regenerated mammary neoplastic lesions in C57Bl/6 mice expressing ERα and Her2. The brown color depicts positive staining of ERα or Her2

Increased inflammation and immune responses in old mammary cells. As the initial step in elucidating cellular pathways that may contribute to the aging-associated transforming phenotype of MaSCs, we compared gene expression profiles between young and old mammary stromal cells and found that the *Cdkn2a* locus, containing p16Ink4a and p19Arf, was the most highly up-regulated transcript in the old stromal cells among all significantly (adjusted P value (aka **FDR**, false discovery rate)<0.05) and differentially regulated genes with a 19-fold difference (see the heatmap in **Fig. 10**). The significant increase of both p16Ink4a and p19Arf in the old stromal cells was confirmed with real time RT-PCR (**Fig. 7**) suggesting a senescence phenotype of the old stromal cells. This is consistent with the old mammary gland expressing higher senescence-associated β -gal activity (**Fig. 8**). We found 66 differentially expressed genes between young and old stromal cells with an adjusted P value of <0.05 (**Fig. 9**).

Functional annotation of these differentially expressed genes with the Database for Annotation, Visualization and Integrated Discovery (**DAVID**)²² platform identified many significantly (P<0.05) altered Biological Processes (**BPs**) depicted as gene ontology (**GO**) terms with the top ten listed in **Fig. 9**. While over 200 genes were found to be differentially expressed between young and old luminal progenitorenriched spheres, DAVID analysis yielded top enriched BPs mostly related to cell adhesion, biological adhesion, and extracellular matrix organization (data not shown) suggesting that aging-associated luminal cell functions are more involved in epithelium structure remodeling with a limited role in the early neoplastic transformation by the old MaSCs. Consequently, we have focused our attention on the altered gene expression in aging stromal cells and MaSCs. Although there are only 7 genes that are differentially regulated during aging in both basal cell-formed mammospheres and stromal cells (**Fig. 9**), the functional annotation revealed that the top enriched Biological Processes in both sets of the genes are related to immune, inflammatory, defense, and wounding responses (**Fig. 9**).

These processes and responses are mostly performed by a shared set of genes in each cell type, which are shown in the heatmaps in **Fig. 10**. Some of the genes associated with the Oxidation Reduction, the top GO term for the stromal gene set, are involved in biosynthesis/production of eicosanoids, which may also contribute to inflammation (**Fig. 10**). We have also observed a significant increase of *Ptgs2* transcript in our RNA-seq data (pointed by the arrow in **Fig. 10**) and its protein COX2 in old mammary gland with immunostaining (**Fig. 14** shown in Aim 2.2), and an increased number of infiltrating macrophages in the old mammary gland (data not shown). Thus, there is an increased senescence-associated inflammation response (**SIR**) in the old mammary glands.

[figure not shown]

Fig. 10. Heatmap of the fold change of significantly (FDR<0.05) differentially expressed genes associated with senescence and top three GO terms shown in Fig. 6 between young and old mammosphere and stromal cells. The genes associated with the three GO terms are marked with the colored vertical bars. Heatmap colors indicate the logarithm of the fold change.

Rapamycin treatment mitigated the aberrant phenotypes of old MaSCs. To investigate whether the increased SIR in the old mammary gland contributes to the increased number and transforming phenotype of the old MaSCs, we tested the efficacy of rapamycin in inhibiting the aging-associated mammary gland dysfunction because it is an anti-inflammatory and immune modulatory drug and its target mTOR is known to be up-regulated in senescent cells²³. Rapamycin was shown to significantly extend lifespan and reduce tumor incidence in mice by investigators in our university as well as by others²⁴. It was also shown recently to inhibit senescent mammary stroma-promoted growth of

xenografted breast cancer cells in a premature aging mouse model with *Cav-1* knockout²⁵. As shown in **Fig. 3B**, old mammary glands have higher percent of MaSCs. Both long-term (2 years) and short-term (5-10 days) treatment with a diet containing eRapa (microencapsulated rapamycin) significantly reduced the frequency of MaSCs in old mice (**Fig. 11A**). More significantly, both long- and short-term treatment also reduced hyperplastic and dysplastic foci not only in the primary old mammary glands but also in the regenerated glands by old MaSCs (**Fig. 11B** and **C**).

[figure not shown]

Fig. 11. Decreased MaSC frequency and early neoplastic foci after rapamycin treatment. Frequency (mean±SD) of MaSC (A) expressed as percent sphere formation and differentiation initiating cell in the basal cell fraction (%SFD-IC_b) in young (blue dots) and old (red dots) mammary glands from C57Bl/6 (2 vs. 26 months), and in long-term (2 yr) and short-term (5-10 day) encapsulated rapamycin (eRapa)-treated (green dots) or control (red dots) old C57Bl/6 mice (26 months of age upon termination). The frequency of pre-neoplastic (expressed as %hyperplasia, B) and neoplastic (%ADH/DCIS, C) lesions in primary (P) and MaSC-regenerated glands (R) of long-term and short-term eRapa-treated (green dots) or control (red dots) mice (26 months of age). Each dot in the plots represents one mouse.

These exciting novel observations prompted us to propose the following research aims.

4. OBJECTIVES

The overall purpose of the study is to evaluate the efficacy of short-term rapamycin treatment on malignant markers and MaSC in patients with DCIS, LCIS, ALH or ADH.

4.1 Primary Objective

- 1. Reduction of MaSC in DCIS, LCIS, ALH or ADH in patients receiving rapamycin
- 2. Reduction of malignant markers in DCIS, LCIS, ALH or ADH in patients receiving rapamycin

4.2 Secondary Objectives

- 1. Toxicity
- 2. Surgical complications

5. PATIENT ELIGIBILITY

5.1 Inclusion Criteria

Subjects must meet all of the following criteria to be eligible for the trial:

- 1. Women with confirmed menopausal status. All patients who have NOT had a prior bilateral oophorectomy and/or are younger than age 60, will require menopausal status verified by FSH and estradiol local labs.
- 3. Women diagnosed with DCIS, LCIS, ALH or ADH lesions detected by pathology
- 4. Women scheduled for mastectomy or lumpectomy after DCIS, LCIS, ALH or ADH diagnosis
- 5. Women consented to the tissue biorepository (HSC20070684H/CTRC# 07-32)

- 6. Women of child-bearing potential willing to practice 2 forms of contraception, one of which must be a barrier method until at least 30 days after the last dose of rapamycin.
- 7. Women of child-bearing potential must have a negative serum pregnancy test at time of enrollment.
- 8. Patients must be able to swallow and retain oral medication.
- 9. All patients must have given signed, informed consent prior to registration on study.
- 10. Patients must have normal organ and marrow function as defined below:
 - a. Leukocytes ≥ 3,000/µL
 - b. Absolute neutrophil count \geq 1,500/µL
 - c. Platelets \geq 100,000/µL
 - d. AST $\leq 2.5 \text{ X ULN}$
 - e. ALT $\leq 2.5 \text{ X ULN}$
 - f. Total bili \leq 1.5 X ULN or Direct bili \leq 1 X ULN

5.2 Exclusion Criteria

- 1. Women who are pregnant.
- 2. Women who are receiving any other concomitant treatment for their DCIS, LCIS, ALH or ADH
- 3. Women who are taking rapamycin for another diagnosis.
- 4. Women with an allergy to rapamycin or its derivatives.
- 5. Active infection requiring systemic therapy.
- 6. Patients who are taking any pills containing herbal (alternative) medicines are NOT eligible for participation. Patients must be off any such medications by the time of registration.
- 7. Immunocompromised subjects, including patients with human immunodeficiency virus
- 8. Women currently taking strong CYP3A4 inducers or inhibitors. Drugs that cannot be coadministered with rapamycin include but are not limited to: Calcium channel blockers: nicardipine, antifungal agents: clotrimazole, fluconazole, antibiotics: troleandomycin, rifapentine, gastrointestinal prokinetic agents: cisapride, metoclopramide, Other drugs: bromocriptine, cimetidine, danazol, HIV-protease inhibitors (e.g., ritonavir, indinavir), anticonvulsants: carbamazepine, phenobarbital, phenytoin. *Appendix 4* has a complete list of these medications.
- 9. Patients with any of the following conditions or complications are NOT eligible for participation:
 - a. GI tract disease resulting in an inability to take oral medication
 - b. Malabsorption syndrome
 - c. Require IV alimentation
 - d. History of prior surgical procedures affecting absorption
 - e. Uncontrolled inflammatory GI disease (e.g., Crohn's, ulcerative colitis)

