10. CONCOMMITANT MEDICATIONS

All concomitant treatments, including blood and blood products, must be reported on the appropriate electronic case report form (eCRF).

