10.1 Not Permitted

Patients who are taking any herbal (alternative) medicines are NOT eligible for participation. Patients must be off any such medications before the first dose of study treatment. Patients who are undergoing concomitant radiotherapy or chemotherapy are NOT eligible for participation.

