12. FOLLOW-UP POST-THERAPY

Patients will be followed 3 months after surgery at the time of routine clinic visit or via phone call with study personnel, See APPENDIX 3 –subsection titled Research Chart (case report form needed for data collection during this 3-month follow-up visit).

Treatment after study completion will be left to the discretion of the treating physician(s) and will not be considered part of this study. However, patients should still be followed for surgical complications as part of their standard of care.

Procedures	Screening & Baseline	Day 1-7 ⁴	Day before Surgery	Surgery ²	3 month Follow-Up
Tissue procurement ¹				Х	
Informed consent	х				
Rapamycin administration		Х			
Cancer history ³	х		х		
Physical exam ³	х		х		
CBC w/ diff	X ³		Х		
Comprehensive metabolic panel	X ³		х		
Lipid panel	х		х		
Estradiol ⁵	Х		х		
FSH⁵	Х		х		
Toxicity (AE) assessment			Х		Х

13. SCHEDULE OF EVENTS

¹ Fresh tissue procurement will be required for study purposes.

² Surgery can take place 3-7 days after completion of rapamycin treatment

- ³ Pre-study laboratory tests, cancer history, and physical exam (including review of systems) must be completed within 28 days prior to registration. At the discretion of the treating physician and only if clinically indicated as part of their standard of care, the pre-study CBC and CMP will be repeated one (1) day prior to treatment administration.
- ⁴ Rapamycin will be administered for 5-7 days
- ⁵ Estradiol and FSH are required only if patient is under 60 years of age and has not had a bilateral oophorectomy.

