17.4 Patient Referrals to the Study

For potential patients please email the Nurse/Research Coordinator prior to consenting a patient to determine whether a slot is available on the study. In order for patient referrals to be processed efficiently, study teams are asked to inform the Nurse/Research Coordinator of any enrollment deadline date, if any.

Once a patient is referred for possible study enrollment, the treating physician will be asked to review, sign and date the study Eligibility Checklist as verification that the patient has met all inclusion/exclusion criteria. It will be the responsibility of the treating physician to issue informed consent to the patient.

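### Exclusion 8 calls Appendix 4 the complete list of drugs barred with rapamycin, but nine of the 15 drugs it names are not there, and 10.1 does not repeat the restriction for the dosing days

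*Combined protocol and SAP*

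**What the plan says.** Section 5.2, Exclusion 8, does three things in sequence. It states a class rule: "Women currently taking strong CYP3A4 inducers or inhibitors" are excluded. It then names drugs by group, introduced by "Drugs that cannot be coadministered with rapamycin include but are not limited to". It closes by sending the reader to Appendix 4, which it says "has a complete list of these medications".

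Appendix 4 is titled as the prohibited strong CYP3A4 agents. Its table has one row of inhibitors and one of inducers.

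Section 10.1 (Not Permitted) covers other treatments: "Patients who are taking any herbal (alternative) medicines are NOT eligible for participation", and "Patients who are undergoing concomitant radiotherapy or chemotherapy are NOT eligible for participation". It mentions neither CYP3A4 agents nor Appendix 4. Section 10.2 (Permitted) allows supportive care, anti-emetics included, at the treating physician's discretion. It names no drug and makes no exception for interacting ones.

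Section 17.4 has the treating physician "review, sign and date the study Eligibility Checklist as verification that the patient has met all inclusion/exclusion criteria".

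**The concern.** The body text gives examples and the appendix is presented as the full list, so every example should be in the appendix. Most are not. A coordinator who takes the pointer at its word and checks a medication list against Appendix 4 would not flag, for instance, fluconazole or cimetidine, although the criterion says neither may be given with rapamycin.

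The dosing days raise a related question. Exclusion 8 is an eligibility criterion and speaks of what a woman is currently taking. The section a clinician would open when prescribing during treatment is section 10, and it does not carry the restriction.

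What is at stake is control of rapamycin exposure. Sections 8 and 14.3 say that adverse events generally depended on dose or concentration. Section 9 allows no dose modification, and the section 13 schedule lists no rapamycin level. Keeping interacting drugs out is therefore an important safeguard, and toxicity is a secondary objective (section 4.2).

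**Working it through.** The plan gives no figure to reproduce. The check is a name-by-name comparison of Exclusion 8 with the Appendix 4 table.

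**Inputs.** Exclusion 8 supplies the named drugs and their groups. Appendix 4 supplies 24 inhibitors and 9 inducers: 24 + 9 = 33 entries.

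| Group in Exclusion 8 | Named | In Appendix 4 | Not in Appendix 4 |
|---|---|---|---|
| Calcium channel blocker | 1 | 0 | nicardipine |
| Antifungals | 2 | 0 | clotrimazole; fluconazole |
| Antibiotics | 2 | 1 (troleandomycin) | rifapentine |
| Prokinetics | 2 | 0 | cisapride; metoclopramide |
| Other | 3 | 0 | bromocriptine; cimetidine; danazol |
| Protease inhibitors | 2 | 2 (indinavir; ritonavir) | none |
| Anticonvulsants | 3 | 3 (carbamazepine; phenobarbital; phenytoin) | none |

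**Totals.**
- Named: 1 + 2 + 2 + 2 + 3 + 2 + 3 = 15.
- In both places: 0 + 0 + 1 + 0 + 0 + 2 + 3 = 6.
- In Exclusion 8 only: 15 - 6 = 9, and 9/15 = 60%.
- Appendix 4 if all nine are added: 33 + 9 = 42 entries.

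**Could the PDF reading explain it?** It is unlikely. The table prints before its heading and its footnote marks have no text, but both drug rows look whole. Each is nearly alphabetical and runs to a natural end (voriconazole; St. John's wort). The nine drugs would fall at scattered points in that order, so one lost block would not remove them all.

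**Could the pointer mean something narrower?** The drugs it refers to could be only the strong CYP3A4 agents, which fits the appendix title. Exclusion 8 would then list nine drugs under its strong-agent rule that its own complete list of strong agents omits. The mismatch remains on either reading, and no other section reconciles the two lists.

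**Dosing period.** Read together, Exclusion 8 bars coadministration, 10.1 is silent on CYP3A4 agents, and 10.2 gives discretion without reference to the rule. The restriction is thus stated once, in the eligibility section.

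**The case against.** The strongest reply is that the nine drugs are already prohibited. Exclusion 8 says they cannot be coadministered, and the physician verifies every criterion, not the appendix alone. The two lists can also be applied cumulatively: no drug is barred in one place and allowed by name in the other. On that view only the claim of completeness is false. This stands, and it limits the point to staff who rely on the appendix by itself.

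Second, the coadministration wording is not tied to enrolment, Appendix 4 is titled as a list of prohibited drugs, and section 17.6 requires the study to be run as the protocol describes. The restriction therefore arguably covers the dosing days already. This also has force. A reader might infer from 10.1 and 10.2 that the nine drugs may be started during dosing, but the documents do not say so. What can be said is that 10.1 does not repeat the rule where a prescriber would look for it.

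Third, Exclusion 5 bars active infection needing systemic therapy, which removes some women who would be on an antifungal or antibiotic. It does not reach topical or preventive use, or the drugs that are not anti-infectives, so it narrows the gap without closing it.

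Finally, the 60% uses an openly illustrative list as its denominator. That is correct: it describes the mismatch between two lists and is not a measure of risk.

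**Conclusion.** The point holds as a minor internal inconsistency in a safety criterion. Nine of the 15 named drugs are missing from the list called complete, and the restriction is not repeated in section 10. The count is exact, provided that the table as extracted is whole apart from its footnotes.

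A reader might go further and infer that women on these drugs would be enrolled, that toxicity would rise, or that the marker results would be distorted. The documents support none of this. They give no figure for use of the nine drugs, and Exclusion 8 bars them. They also do not show which of the nine are strong CYP3A4 agents, so the review cannot say that the appendix is pharmacologically wrong under its present title.

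Safeguards during the trial are partial. Concomitant treatments go on the eCRF (section 10), and laboratory tests and "Toxicity (AE) assessment" are scheduled for the day before surgery (section 13). These would record a coadministered drug or its effects but would not prevent it. No sample size, power, significance level or analysis is affected.

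**What to change.** 1. **Appendix 4.** The protocol already says that the nine drugs cannot be given with rapamycin, so add them (33 to 42 entries) and retitle the appendix as drugs prohibited with rapamycin. The present title restricts it to strong agents and may not fit all nine. At minimum, replace the sentence claiming completeness with: *in addition to the drugs above, see Appendix 4*.
2. **Section 10.1.** State that the drugs in Exclusion 8 and Appendix 4 are not permitted from registration through the last rapamycin dose.
3. **Section 10.2.** Make supportive care, including anti-emetics, subject to that rule.
4. **Eligibility Checklist (17.4).** Point it to the same reconciled list.

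The cost is a minor protocol clarification and a checklist update. The design and analysis are unchanged.
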